8.3.5. Web-based Maintenance Intervention Usage Data

The data will be transferred from the University of Nottingham to the University of York using secure file transfer protocol. IP addresses and location information of participants will not be stored or transferred.

8.4. Access to Data

Direct access will be granted to authorised representatives from the Sponsor, host institution and the regulatory authorities to permit study-related monitoring, audits and inspections. The research team includes collaborating investigators from outside of the Sponsor/host institution who may require access to data (including personal data).

York Trials Unit will have access to data entered by the participating NHS Trusts (screening and enrolment logs, consent forms, clinical assessment CRFs, participant contact details), healthcare professionals (intervention attendance records) and University of Nottingham research team (participant questionnaire data).

York Trials Unit will provide access to limited datasets for research staff at the University of Nottingham to enter and review questionnaire management data and to update participant contact details and enter and update HCP contact details. Research staff at UoN will require access to participant contact details to update these as necessary and to contact participants to provide the follow-up questionnaires and reminders. HCP contact details are required for arranging of REDUCE sessions. The University of Nottingham research staff will enter the participant questionnaire data into a secure database held on University of Nottingham Microsoft cloud-based servers, backed up regularly and accessible by those on the delegation log, via usernames and passwords. YTU will receive and transfer the questionnaire data for analysis using their secure encrypted drop off service.

York Trials Unit will receive the web-usage data from the University of Nottingham research team and will provide to the University of Edinburgh, King's College London and Swansea University research teams.

The University of Edinburgh research team will require access to the contact details of intervention participants and HCPs to arrange and conduct the interviews. This will be provided by York Trials Unit using an encrypted Microsoft Excel spreadsheet, sent using the University of York secure encrypted drop off service. The University of Edinburgh will share de-identified data from the

interviews, e.g. quotes and themes with the University of Nottingham, Swansea University and King's College London research teams where appropriate to the analyses.

The Swansea University research team will require access to the de-identified questionnaires, clinical assessments and resource use data. This will be provided by York Trials Unit using the University of York secure encrypted drop off service.

The King's College London research team will require access to healthcare professionals' contact details, home practice questionnaire results and website usage data.

The TMG and TSC will have sight of relevant de-identified aggregate data as part of their oversight at the management group and steering committee.

8.5. Archiving

At the end of the study, following completion of the end of study report, York Trials Unit will securely archive all centrally held study related documentation in the Trial Master File for a minimum of five years. At the end of the defined archive period arrangements for confidential destruction will be made.

It is the responsibility of each PI to ensure that data and all essential documents relating to the study are retained securely for a minimum of five years after the end of study, and in accordance with national legislation. In conjunction with the Sponsor, York Trials Unit will notify sites when study documentation held at sites may be archived, and then destroyed. All archived documents must continue to be available for inspection by appropriate authorities upon request.

9. STATISTICS AND HEALTH ECONOMICS

9.1. Sample Size Calculation

This study is an external pilot RCT and as a result the sample size has not been calculated to assess the effectiveness of the intervention. We will enlist two sites to recruit 15-20 participants over a three month period. This would mean a recruitment yield of approximately four participants per site per month, which is comparable to the yield we would require in a main trial, and will provide an opportunity to determine whether recruitment estimates need to be refined. In addition, this sample size, together with a 2:1 allocation ratio, will provide a sufficient number of intervention participants for the qualitative study.

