	Tower Building, University of Nottingham, [name]					
	[contact]					
	Email: [contact]					
Sponsor:	University Hospitals of Derby & Burton NHS Foundation Trust					
	Royal Derby Hospital, [name]					
	[contact]					
	Email: [contact]					
Funder(s):	NIHR Programme Grants for Applied Research					
	NIHR Central Commissioning Facility					
	Email: [contact]					
	[contact]					
Trial Manager	[name]					
	York Trials Unit					
	Department of Health Sciences, University of York					
	[name]					
	[contact]					
	Email: [contact]					
Clinical Trials Unit:	York Trials Unit					
	Department of Health Sciences, University of York, [name]					
	[contact]					
Statistician:	[name]					
	York Trials Unit					
	Department of Health Sciences, University of York, [name]					
	[contact]					
	Email: [contact]					
Health Economist	[name]					
	College of Human and Health Sciences, Room: SCHE – 218,					
	[name]					
	[name]					
	[contact]					
	Email: [contact]					

STUDY SUMMARY

Study Title:	Reducing the impact of diabetic foot ulcers: Pilot trial						
Short Title:	Reducing the impact of DFUs: Pilot trial						
Sponsor Reference:	UHDB/2020/037						
Study Design:	Multi-centre randomised controlled pilot trial with nested qualitative study						
Study Participants:	Pilot trial: People with diabetes, two lower limbs and a recently healed DFU (fully epithelialised with no drainage, for a minimum two weeks). Nested qualitative study: Intervention participants and healthcare professionals delivering REDUCE.						
Planned Number of Sites:	Two secondary care NHS Trusts will recruit patients and deliver the intervention. Follow up data will be collected from secondary care, primary care and community health including podiatry and wound care medical records.						
Planned Sample Size:	N=23, consisting of: 20 participants and three healthcare professionals						
Treatment Duration:	3 months						
Follow Up Duration:	4 months						
Planned Start Date:	19/04/2021						
Planned Recruitment End Date:	18/07/2021						
Planned Study End Date:	31/03/2022						

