4. STUDY SETTING

This is a multi-centre randomised controlled pilot trial involving at least two clinical sites recruiting 15-20 participants (i.e., 7-10 participants per site). It is anticipated that the participant population will be recruited from specialist multidisciplinary diabetic foot clinics at participating secondary care NHS Trusts. The intervention will be undertaken at the participating Trusts.

Usual care for both arms of the study will be provided by the clinical care teams in primary care, secondary care and community health including community podiatry teams.

Clinical outcome data will be extracted from any relevant healthcare records including (but not limited to) primary care, secondary care, community health and podiatry records.

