6. PROCEDURES

6.1. Recruitment

6.1.1. Participant Identification

6.1.1.1 Pilot Trial Participants

Over a three-month recruitment period potential participants will be identified from and screened by their clinical care team in specialist multidisciplinary diabetes foot clinics at the participating NHS Trusts. Medical records will be accessed only by a member of the existing clinical care team (not by the research team) in order to establish whether they are eligible to be invited to take part in the study. No details about patients will be passed on to the research team at this stage.

Potential participants on clinical caseloads will be screened against the eligibility criteria in the pilot trial sites. Those eligible will be approached about the trial by their usual clinical carers and given some details about the study, including an information sheet. Participants will be provided with information regarding the trial as soon as possible after healing of all their foot ulcers, but will only be recruited and consented at a separate clinic visit after the ulcer has remained healed for a period of at least two weeks (i.e., clinical definition of healing).

It will be clearly stated that the potential participant is free to withdraw from the study at any time for any reason without prejudice to future care, and with no obligation to give a reason for withdrawal. Should new information arise during the study, which may affect a participant's willingness to take part, this will be reviewed for addition to the participant information sheet and a revised consent form will be completed as necessary.

The potential participant will be allowed as much time as they wish to consider the information, and will be given the opportunity to question the Principal Investigator, the research team, their GP or other independent parties to decide whether they will participate in the study.

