9.2. External Pilot Stop-Go Criteria

Recruitment and data collection will be assessed against pre-defined stop-go criteria The primary criterion is the number of participants recruited, with the secondary criterion being the collection of primary and secondary outcome data (as measured by extraction of relevant data from clinical records related to the primary outcome and questionnaire return rates).

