9.3. Planned Recruitment Rate

A planned recruitment rate is not required for this pilot feasibility study.

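### The recruitment yield of about four per site per month in section 9.1 does not follow from the protocol's own target, sites and period, which give 2.5 to 3.3

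*Protocol*

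**What the plan says.** Protocol section 9.1 sets the size of the pilot: "We will enlist two sites to recruit 15-20 participants over a three month period". It then draws a rate from that plan and compares it with the main trial's need: "This would mean a recruitment yield of approximately four participants per site per month, which is comparable to the yield we would require". The section says that the sample size was not calculated to assess effectiveness. The yield is therefore the main numerical reason given for the pilot's size; the only other reason is having enough intervention participants for the qualitative study.

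Other parts of the protocol give the same inputs:

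- Section 4 describes "at least two clinical sites recruiting 15-20 participants (i.e., 7-10 participants per site".
- Section 6.1.1.1 confirms the period: "Over a three-month recruitment period potential participants will be identified from and screened by their clinical care team".
- The Study Summary gives recruitment dates of 19/04/2021 to 18/07/2021 and a planned sample of "N=23, consisting of: 20 participants and three healthcare professionals".

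On use of the result, section 9.2 states: "The primary criterion is the number of participants recruited". Section 9.3 states: "A planned recruitment rate is not required for this pilot feasibility study". Section 1.3 says that the pilot will inform the number of centres and the recruitment period of the main trial.

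**The concern.** The figure of four is presented as a consequence of the preceding sentence, not as a separate assumption, and it is not what that sentence implies. The same sentence ties it to what the main trial would require.

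Recruitment feasibility is the first objective in section 2.1, and recruitment rates are a key outcome in section 9.5. A reader who takes section 9.1 at face value could treat a met target of 15 to 20 as support for a yield of about four, when the target corresponds to a lower one. If that reading were carried into the main trial, the number of centres or the length of recruitment could be set too low.

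**Working it through.** **Inputs**

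- Sites: 2 (section 9.1; section 4 says at least two).
- Target: 15 to 20 participants (sections 4 and 9.1); 20 in the Study Summary.
- Period: 3 months (sections 6.1.1.1 and 9.1).
- Stated yield: about 4 per site per month (section 9.1).

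**Attempt to reproduce the stated yield**

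Yield = participants / (sites × months), with 2 × 3 = 6 site-months.

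- Lower target: 15/6 = 2.5.
- Upper target: 20/6 = 3.33.

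In reverse, participants needed = yield × sites × months = 4 × 2 × 3 = 24. Against 24, the target is short by 1 − 20/24 = 17% to 1 − 15/24 = 37.5%. The yield rounds to four only from 3.5 × 6 = 21 participants upward.

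**Other readings of the inputs**

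- Section 4's 7 to 10 per site: 7/3 = 2.3 to 10/3 = 3.3.
- Calendar dates: 19/04/2021 to 18/07/2021 is 91 days inclusive, or 91/30.4375 = 2.99 months. This gives 15/(2 × 2.99) = 2.5 to 20/(2 × 2.99) = 3.3.
- Three sites, allowed by section 4: 15/9 = 1.7 to 20/9 = 2.2. More sites lower the yield further.
- All 23 people in the Study Summary: 23/6 = 3.83. This is close to four, but it counts three healthcare professionals as recruited patients. The protocol does not say that the figure arose this way.

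No legitimate reading gives four.

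**Size of the gap if the main trial needs four (assumption)**

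- Share of the need shown when the target is met over the full period: 2.5/4 = 62.5% to 3.33/4 = 83%.
- Increase in site-months relative to a plan at four: 4/3.33 = 1.2 to 4/2.5 = 1.6 times.

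**Precision of the observed yield**

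The exact Poisson 95% limits for a count n are chi-square(0.025; 2n)/2 and chi-square(0.975; 2n + 2)/2. Dividing by 6 site-months gives:

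- n = 15: count limits 8.40 and 24.74, so yield 2.5 (1.4 to 4.1).
- n = 20: count limits 12.22 and 30.89, so yield 3.3 (2.0 to 5.1).

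Both intervals include four.

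**Effect of finishing early**

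At four per site per month, two sites recruit 8 a month. They would reach 20 in 20/8 = 2.5 months and 15 in 15/8 = 1.9 months.

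**The case against.** The strongest reply accepts the arithmetic and disputes the consequence.

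- **Planning input.** Sections 1.3 and 9.5 make the observed recruitment rate the information carried forward, and section 9.1 itself says that the pilot will show whether recruitment estimates need refining. If 20 people are recruited in 6 site-months, the observed rate is 3.3 whatever section 9.1 says. This stands. A reader might infer that the main trial will open with too few site-months, but the protocol does not say that it will be sized from the figure of four. Harm arises only if a met target is taken as confirmation of that figure.
- **Main-trial requirement.** The protocol says only that about four is comparable to the requirement. This stands. If the requirement is nearer three, the error is confined to one figure in section 9.1.
- **What a successful pilot can show.** A reader might infer that a pilot that meets its target cannot show four. That is too strong: 20 recruits in 2.5 months would show exactly four, and the intervals for 15 and 20 recruits over the full period do not exclude it.
- **Section 9.3.** A reader might infer that it contradicts the stop-go criterion. It does not, because section 9.2 uses a number recruited, not a rate. The narrower point remains that section 9.3 disclaims a planned rate while section 9.1 states one.
- **Method of reporting.** The interval method is a detail that a statistical analysis plan may properly hold, so its absence from the protocol is no fault.

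None of this rescues the printed yield. It is stated as a derivation, the inputs agree across the document, and the word approximately does not cover a shortfall of 17% to 37.5%.

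**Conclusion.** The error in section 9.1 is unconditional: the protocol's own inputs give 2.5 to 3.3 participants per site per month (2.3 to 3.3 from section 4's per-site range), and a yield of four would need 24 participants.

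The consequence for the main trial is conditional on three assumptions: that the main trial needs about four, that its site-months are planned at four, and that the pilot target is met over the full three months and not early. On those assumptions the point estimate reaches 62.5% to 83% of the need, and site-months would have to rise 1.2 to 1.6 times. With 15 to 20 recruits in 6 site-months the pilot could neither establish nor exclude a yield of four.

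This is a wrong figure in the sample-size rationale. It should be corrected, but it is not critical: it changes no participant number, procedure, outcome or analysis.

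**What to change.** - **Section 9.1:** replace the stated yield with 2.5 to 3.3 participants per site per month. Give the main trial's required yield as a number, and say whether the pilot target falls below it.
- **Section 9.3:** align the text with the rate stated in section 9.1.
- **Main-trial planning:** state that centres and duration will be based on the observed yield, calculated as recruits divided by site-months actually open, and not on whether the 15 to 20 target was met. Ideally report the yield with its interval; the method can sit in the statistical analysis plan.

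The cost is a wording amendment with no extra participants. The stated yield becomes less favourable, and the team has to commit to a figure for the main trial's requirement.

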9.2. External Pilot Stop-Go Criteria

Recruitment and data collection will be assessed against pre-defined stop-go criteria The primary criterion is the number of participants recruited, with the secondary criterion being the collection of primary and secondary outcome data (as measured by extraction of relevant data from clinical records related to the primary outcome and questionnaire return rates).

9.3. Planned Recruitment Rate

A planned recruitment rate is not required for this pilot feasibility study.

9.4. Statistical Analysis

A statistical analysis plan (SAP) giving details of the planned analyses will be drafted before data collection has been completed, and reviewed by the Trial Management Group and the Trial Steering Committee. A brief description of the planned analyses is given below.

The statistical analysis will be carried out by a statistician at York Trials Unit, using Stata v16 or later. The analysis and reporting of this pilot trial will follow CONSORT guidelines [34,35]. A flow diagram will be produced, depicting the flow of participants through the trial. The number of participants screened, eligible, consenting and randomised will be summarised, with reasons for ineligibility and non-consent given where available.

Baseline data will be summarised by randomised group, with no formal statistical comparisons being undertaken [36]. Continuous variables will be summarised using descriptive statistics (n, mean, standard deviation, median, minimum, maximum), while categorical variables will be summarised using counts and percentages. Participant outcomes will be summarised descriptively by randomised group and time point, including the amount of missing data. This study is a pilot trial, and as a result statistical hypothesis testing of outcomes will not be carried out.

For the intervention group, attendance of the one-to-one sessions and use of the web-based maintenance intervention will be summarised descriptively.

Adverse events will be summarised descriptively by treatment group.

9.5. Outcome Measures

The primary outcome for a future main clinical and cost-effectiveness trial will be 'ulcer-free time with limbs intact'. The secondary outcomes are:

- Clinical: days to re-ulceration; number of ulcers; days in hospital; amputations, mortality.
- Psychological/behavioural risk factors targeted in REDUCE to examine mechanisms and economic outcomes to examine cost-effectiveness.

The pilot will allow trial procedures (e.g., recruitment, randomisation, delivery of the intervention and collection of outcome measurements) to be tested prior to the main effectiveness trial. The key outcomes of the external pilot trial will include:

- rates of recruitment and retention
- data on the viability and variability of primary and secondary outcome data collection;
- nature and extent of any modifications to the REDUCE intervention, training programme, logic model, mixed-methods process evaluation data collection methods and/or intervention fidelity tool.

9.6. Health Economic Analysis

The baseline and three-month information on resource use and patient reported outcomes will be analysed (e.g. EQ-5D and ICECAP-A) to assess whether the measures can be completed by participants and/or research team (e.g. completion rates, missing items). We will use the information from this pilot trial, alongside the previous work where we obtained perspectives from commissioners and service providers and conducted *think aloud* interviews to finalise a framework for the economic evaluation for the main trial including a first draft of the health economics analysis

plan (HEAP). We anticipate that careful attention to these design and conduct issues will reduce bias and enhance the accuracy, reliability and completeness of data for a full economic analysis within the main trial.

9.7. Qualitative Data Analysis

All interviews will be recorded, transcribed and analysed, potentially using a combination of thematic and framework analysis and critical incident techniques [37,38]; we may also try out other data analysis approaches at this stage in order to inform decisions about the most appropriate analytical approaches to use in the main trial process evaluation.

9.8. Fidelity Assessment Data Analysis

The intervention session fidelity tool data will be analysed descriptively. The data will be analysed descriptively with analysis for inter-rater reliability.

10. MONITORING, AUDIT & INSPECTION

The Investigator(s) must ensure that source documents and other documentation for this study are made available to study monitors, the REC or regulatory authority inspectors. Authorised representatives of the Sponsor and YTU may visit the participating sites to conduct audits/inspections as indicated in the Sponsor's risk assessment of the study.

Monitoring and source data verification will be conducted by YTU on behalf of the Sponsor according to the study monitoring plan. The extent and nature of monitoring will be determined by the study objectives, purpose, design, complexity, blinding, number of patients and sites, and endpoints.

The Sponsor may suspend or prematurely terminate either the entire study, or the study at an individual site, for significant reasons that must be documented (e.g. an unacceptable risk to participants or serious repeated deviations from the protocol/ regulations). If this occurs the Sponsor shall justify its decision in writing and will promptly inform any relevant parties (i.e. participants, investigators, participating sites, REC, regulatory bodies).

A study specific monitoring plan will be developed to outline any monitoring or audit considerations.

11. ETHICAL AND REGULATORY CONSIDERATIONS

11.1. Assessment and Management of Risk

No formal monitoring visits will be planned for this study. A monitoring plan will however be generated for the study, to outline the range of centralised monitoring activities (e.g. eligibility, consent, safety checks), which will be undertaken in this study.

11.2. Peer Review

This study has been peer reviewed as part of the NIHR PGfAR application process.

11.3. Public and Patient Involvement

Patients and carers have been involved in the design of the pilot trial and will be involved in the management of the research, analysis of results and the dissemination of findings. Our participant information sheet has been co-developed with our patient and public involvement (PPI) group. In addition, members of the PPI group have provided feedback on the content of the digital and handbook versions of the MI and have tested the feasibility and duration for completing the psychological, behavioural and health economic questionnaires.

The PPI group will meet three times per year. The group will also be consulted on the findings of this pilot trial and their advice will be sought regarding any changes required for the main clinical and cost-effectiveness trial.

